Although ePRO questionnaires have been widely studied in the general clinical setting it is yet to be proven that they are as effective as paper PRO questionnaires at collecting data within clinical trials where there are additional research ethics, research governance and regulatory requirements to comply with. Our study will pilot implementation of ePRO collection within ICR-CTSU trials and generate evidence regarding its equivalence to paper-based collection. This research will investigate whether ePRO questionnaires can be used within multicentre clinical trials and reduce the burden of clinical trial follow up on patients, allowing patients to participate in quality of life follow up with the minimum possible inconvenience at a time when the patient is already under the stress of being unwell. If this is the case the impact could allow for more comprehensive quality of life study recruitment and responses, helping ensure the patient experience is captured as accurately as possible over the appropriate duration of time.

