2.2. SECONDARY OBJECTIVES

- To investigate whether there are differences in response scores between the two modalities (electronic and paper) at key time points (e.g. due to convenience of returning ePRO questionnaires more severe PRO issues may be identified electronically).
- To assess whether there are differences in return rates (compliance) between paper and electronic questionnaires at later questionnaire time points.
- To investigate whether there are differences in number of items completed within a questionnaire (completeness) between electronic and paper questionnaires.
- To investigate whether there are differences in satisfaction between participants filling out electronic or paper questionnaires
- To investigate whether there are any demographic differences between people who agree to be randomised and those who choose to complete questionnaires electronically or on paper
- To investigate whether changes in response scores from baseline (paper questionnaire) to follow-up vary according to modality of follow-up questionnaire completion.
- To investigate the time taken to distribute paper questionnaires compared to electronic questionnaires.
- To assess the requirement to remind patients to fill in paper and electronic questionnaires.

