4.2. SECONDARY ENDPOINTS

- Domain scores and item responses at key QoL host trial time points.
- Compliance with questionnaire completion at all further time points of QoL collection within the host trial.
- Completeness of data (% of questions filled in within the questionnaire) in the host trial's primary QoL questionnaire.
- Patient satisfaction with electronic and paper questionnaires.
- Patient demographics in each group
- Change in response scores from baseline.
- Time taken (minutes) to prepare a paper questionnaire for distribution compared to electronic dispatch.
- % of patients sent reminders to complete questionnaires for paper and electronic questionnaires.

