7. STUDY ASSESSMENTS

7.1. PRIOR TO STUDY ENTRY

All participants should complete their baseline questionnaire booklet on paper.

For format A studies the host trial's approved baseline booklet should be completed by SPRUCE participants as part of the host trial entry procedure and in accordance with instructions in the host trial's protocol.

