For the secondary outcomes of questionnaire compliance at further time-points and data completeness, percentages between groups at each time-point will be tabulated. Questionnaire domain scores will be calculated as per guidance for each specific measure (e.g. the global health/overall quality of life score from the EORTC QLQ-C30), and compared between electronic questionnaires and paper questionnaires at each time-point using descriptive statistics appropriate for the distributions (e.g. means or medians for numeric scales and percentages for categorical outcomes). Completeness of data and change in domain scores from baseline will be calculated for each follow-up time point, and described between the electronic and paper questionnaire groups. Patient satisfaction with each questionnaire modality and patient demographics across groups (randomised, chose electronic and chose paper) will be captured via patient completed questionnaire and summarised descriptively. Time taken to distribute questionnaires and proportion of reminders sent will also be described. Where appropriate further statistical tests will be used to compare electronic and paper groups for the secondary endpoints including t-tests or Mann-Whitney tests for continuous data. For ordinal data, the chi-squared test for trend will be used. Chi-squared tests will be used for categorical data; Fisher's exact will be used if assumptions of chi-squared are not met.

Further details of analysis methods will be specified in a Statistical Analysis Plan in accordance with ICR-CTSU Standard Operating Procedures.

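### For the randomised cohort the protocol names only unadjusted two-sample tests for questionnaire scores; adjusting for the paper baseline would be more precise at almost no cost

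*Protocol*

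**What the plan says.** Two secondary objectives in Section 2.2 concern scores: "To investigate whether there are differences in response scores between the two modalities (electronic and paper) at key time points" and "To investigate whether changes in response scores from baseline (paper questionnaire) to follow-up vary according to modality of follow-up questionnaire completion". Section 4.2 lists "Change in response scores from baseline" as an endpoint.

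Section 8.3 gives the analysis. Domain scores are to be "compared between electronic questionnaires and paper questionnaires at each time-point using descriptive statistics appropriate for the distributions", and "change in domain scores from baseline will be calculated for each follow-up time point, and described between the electronic and paper questionnaire groups". Where judged suitable, "further statistical tests will be used to compare electronic and paper groups for the secondary endpoints including t-tests or Mann-Whitney tests for continuous data". Regression adjustment is named in the same section, but only for the comparison between preference groups. It covers demographics and clinical characteristics; the baseline score is not mentioned.

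On the data available, Section 7.1 states: "All participants should complete their baseline questionnaire booklet on paper". This comes before study entry, so before the modality is allocated. Section 8.2 minimises the randomisation on age, sex and host trial. The Introduction says that the study will "generate evidence regarding its equivalence to paper-based collection". The only pre-set margin is the 10-point one for compliance at the first post-intervention time point (Sections 8.1 and 8.3).

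**The concern.** A pre-allocation measurement of the same score is usually the best single predictor of the follow-up score. A two-sample test on follow-up scores does not use it. A test on raw change subtracts it in full, which adds noise when the correlation is modest. Neither test uses the minimisation factors. The randomised cohort, where the comparison is cleanest, therefore has the less efficient named method, while regression is kept for the non-randomised cohort.

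At stake is the width of the interval around any mode effect on scores. With a wide interval, a real difference between electronic and paper scores is easier to miss, and a non-significant result says little about agreement.

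**Working it through.** **The protocol's own figure.** 244 randomised patients come from the compliance comparison (90% in both arms, 10-point margin, 80% power, one-sided alpha 0.05). The Farrington-Manning method, with null rates of 0.831 and 0.931, gives

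n per arm = (1.645 × √(0.831×0.169 + 0.931×0.069) + 0.842 × √(2×0.9×0.1))² / 0.10² = (1.645×0.452 + 0.842×0.424)² / 0.01 ≈ 121.1, rounded up to 122, so 244 in total.

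The figure is reproduced. (The simple unpooled formula gives 112 per arm, 224 in total.) It was not chosen for scores.

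**Inputs for scores.** About 110 returned questionnaires per arm (122 × 0.90 = 109.8). The score SD and the baseline-to-follow-up correlation ρ are not in the protocol. I assume SD = 1, equal at both times, and ρ from 0.3 to 0.7.

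**Variance per patient**, in units of the follow-up variance: follow-up score 1; raw change 2(1 − ρ); baseline-adjusted (ANCOVA) 1 − ρ². Hence ANCOVA relative to follow-up is 1 − ρ², and relative to change is (1 + ρ)/2.

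| ρ | Follow-up | Change | ANCOVA | ANCOVA vs follow-up | ANCOVA vs change |
|---|---|---|---|---|---|
| 0.3 | 1 | 1.40 | 0.91 | 9% less | 35% less |
| 0.5 | 1 | 1.00 | 0.75 | 25% less | 25% less |
| 0.7 | 1 | 0.60 | 0.51 | 49% less | 15% less |

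Below ρ = 0.5, raw change is less precise than the follow-up score alone. ANCOVA has the lowest variance of the three throughout this range.

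**In interval width and power.** On raw follow-up scores the standard error is √(2/110) = 0.135 SD. The 95% half-width is 1.96 × 0.135 = 0.26 SD, and the difference detectable with 80% power is (1.96 + 0.842) × 0.135 = 0.38 SD. With ANCOVA the half-width is multiplied by √(1 − ρ²), giving 0.25, 0.23 and 0.19 SD at ρ = 0.3, 0.5 and 0.7.

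Power for a true 0.3 SD difference (two-sided 0.05):

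| ρ | Follow-up | Change | ANCOVA |
|---|---|---|---|
| 0.3 | 60% | 47% | 65% |
| 0.5 | 60% | 60% | 73% |
| 0.7 | 60% | 82% | 88% |

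**Reading a null result.** On raw follow-up scores, the test is non-significant about 40% of the time at a true 0.3 SD difference and 68% of the time at 0.2 SD.

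**The case against.** A reader might infer from the named tests that the baseline is ignored. The protocol does not support that. Change from baseline is an endpoint with its own objective, is calculated at every follow-up, and may itself be tested. The defect is the inefficient use of baseline in a change score, and its absence from tests on follow-up scores.

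A reader might also infer that these tests are meant to supply the equivalence evidence promised in the Introduction. That sentence is about electronic collection in general. Section 1.1 regards score equivalence as already well studied and names compliance and completeness as the gaps. Compliance has a margin and a confidence-interval rule. The score objectives ask about differences, which difference tests suit, and nowhere does the protocol say that a null score test will be taken as equivalence. What stands is a caution against that reading.

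Nor do the documents require the 10-point margin at later time points: Section 8.1 justifies it only at the first one.

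Finally, the tests are conditional, the list is not exhaustive, scores are mainly described, and details are left to a SAP that is not available here and may already name an adjusted model. This lowers the weight of the point. It does not remove it, because the protocol does name the methods for continuous secondary endpoints in the randomised cohort, and they are the less precise ones.

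**Conclusion.** The point holds as one of precision on secondary endpoints. Omitting the baseline does not bias the randomised comparison, and the unadjusted tests are valid; they use the data less well than they could. For correlations of 0.3 to 0.7, the variance saved is 9% to 49% against follow-up scores and 35% to 15% against raw change. At 0.5 the gain equals that from about a third more patients (1/0.75 = 1.33). These figures rest on an assumed correlation, equal SDs at both times and about 110 returns per arm. Radiotherapy lies between baseline and the first follow-up, so the lower end of the range is plausible; there the gain over follow-up scores is small but the gain over raw change is largest. The primary analysis and the sample size are unaffected.

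**What to change.** Where scores are formally compared in the randomised cohort, replace the t-test or Mann-Whitney test on follow-up and change scores with a linear model for each domain and time point: follow-up score on modality, baseline score, age and host trial, plus sex where it varies (all three listed host trials are in prostate cancer). Report the adjusted difference with a confidence interval, by bootstrap if the scores are skewed. One estimate serves both score objectives, because with baseline in the model the modality coefficient is the same whether the outcome is follow-up score or change. EPIC-26, IPSS and IIEF-5 are used in all three host trials, so these instruments can be pooled with host trial as a factor.

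Add a sentence that a non-significant score difference will not be interpreted as equivalence of scores. For compliance at later time points, a difference with a confidence interval is enough.

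The cost is a change of wording and routine code; every variable is already collected. The small downside is that participants with a missing baseline need a simple baseline imputation, which should be specified in advance.

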8.4. INTERIM ANALYSES AND STOPPING RULES

The number of patients opting for a preference rather than allocation via minimisation will be monitored monthly and assessed after 50 patients have been recruited. If greater than 50% of participants have declined allocation via minimisation, or subsequently declined allocated modality, consideration will be given to ceasing randomisation and adopting an alternative recruitment and analysis strategy.

The overall feasibility of recruitment for the study will be monitored and re-evaluated if a third of the required patients have not been recruited within 6 months of the study commencing. If recruitment was an issue at that point, the decision to increase the number of sites that the SWAT is run at or to embed the SWAT into further ICR-CTSU trials could be taken to improve recruitment.

Impact of SPRUCE on PRO uptake and drop out in host trials will be monitored to ensure that PRO data collection within the host trial is not adversely affected by the SWAT. Under format A this will consider the number/proportion of patients consenting to provide PRO data pre and post implementation of SPRUCE.

An interim analysis to review emerging data is planned between 12-18 months after the trial opens and will include the facility to include data in a confidential PhD thesis. Analyses will follow the main statistical analysis plan, although may be largely descriptive if the number of patients are insufficient for formal statistical analysis. Results will be confidential and only for the purposes of the PhD.

9. STUDY MANAGEMENT

9.1. STUDY MANAGEMENT GROUP (SMG)

A Study Management Group (SMG) will be set up and will include the Chief Investigator, ICR-CTSU Scientific Lead, Co-investigators and identified collaborators, the Study Statistician and Study Manager. Principal Investigators and key study personnel will be invited to join the SMG as appropriate to ensure representation from a range of sites and professional groups. Membership will include a lay/consumer representative. The SMG will meet at regular intervals, and at least annually. Notwithstanding the legal obligations of the Sponsor and Chief Investigator, the SMG have operational responsibility for the conduct of the study. The Committee's terms of reference, roles and responsibilities will be defined in a charter issued by ICR-CTSU.

9.2. PATIENT AND PUBLIC OVERSIGHT COMMITTEE

A patient and public oversight committee will be constituted from members of the focus groups which advised on SPRUCE study design. This committee will meet at regular intervals to oversee the study from a PPI perspective and advise on any issues as they arise. They will also help with dissemination of results through their links with national PPI groups and other routes as appropriate.

10. RESEARCH GOVERNANCE

10.1. SPONSOR RESPONSIBILITIES

The Sponsor of this study is the Institute of Cancer Research (ICR).

10.2. PARTICIPATING SITE RESPONSIBILITIES

Responsibilities delegated to participating sites are defined in an agreement between the Sponsor and the individual site. The Principal Investigator is responsible for the trial team and trial conduct at the participating site.

11. TRIAL ADMINISTRATION & LOGISTICS

11.1. SITE ACTIVATION

Before activating the trial, participating sites are required to sign the organisational information document (OID) accepting responsibility for all trial activity which takes place within their site.

Sites may commence recruitment once the OID has been signed by all required signatories, the required study documentation is in place (as specified by ICR-CTSUS) and a site initiation has taken place.

11.2. DATA ACQUISITION

Participants will complete an initial questionnaire booklet on paper, then further questionnaires will be completed in accordance with their randomly allocated or preferred format. All participants will be sent a demographics questionnaire following study entry.

Participants completing questionnaires electronically will receive invitations at the required time points, with a personalised email link sent to the patient for electronic questionnaire completion. ICR-CTSUS will provide guidance to participants to aid the completion of questionnaires. If the questionnaires are not returned within a reasonable time frame, a reminder email will be sent to participants. If two consecutive questionnaires are not completed within a reasonable time frame, a change in participation email will be sent, prompting the participant to inform the ICR-CTSUS team if they no longer wish to participate in the study.

Participants completing questionnaires on paper will receive booklets by post by the ICR-CTSUS following confirmation from the participating site that the patient is alive and able to fill in the questionnaire. Completed booklets will be posted to ICR-CTSUS for data entry. If the questionnaires are not returned within a reasonable time frame, a reminder letter will be sent to participants. If two consecutive questionnaires are not completed within a reasonable time frame, a change in participation letter and form will be sent, prompting the participant to inform the ICR-CTSUS team if they no longer wish to participate in the study.

If necessary, ICR-CTSUS may ask sites to administer the questionnaire for the first post-intervention time point.

A participant satisfaction survey will be sent by ICR-CTSUS to all participants for completion on paper 14 months after joining the study.

11.3. PATIENT TRANSFER

If a participant is transferred within their host trial for clinical follow up at a site not participating in SPRUCE, it remains the responsibility of the original SPRUCE site to respond to health checks or other potential queries from ICR-CTSUS. If the participant is transferred to a site participating in SPRUCE, the ICR-CTSUS should be notified to transfer SPRUCE site.

11.4. CENTRAL DATA MONITORING

Questionnaires with missing data will not be returned to participants for completion as responses should relate to the timeframe specified on the individual questionnaires (e.g. EORTC QLQ-C30 concerns symptoms within the past week). Additionally, data completeness is a secondary endpoint within SPRUCE. Nevertheless, missing data will be monitored regularly to check that there are no issues with the electronic data capture system for example.

11.5. COMPLETION OF THE STUDY AND DEFINITION OF STUDY END DATE

The study end date is deemed to be the date of last data capture.

11.6. ARCHIVING

Essential study documents should be retained according to local policy and for a sufficient period for possible inspection by the regulatory authorities (at least 5 years after the date of last data capture). Documents should be securely stored and access restricted to authorised personnel.

12. PATIENT PROTECTION AND ETHICAL CONSIDERATIONS

12.1. RISK ASSESSMENT AND APPROVAL

This study has been formally assessed for risk and approved by the Sponsor's Committee for Clinical Research.

12.2. PUBLIC AND PATIENT INVOLVEMENT

The need for robust PPI has been recognised from the outset of the ICR-CTSUs ePRO implementation project. The patient and public involvement plan for this work commenced prior to implementation of the SWAT and will continue throughout the project

An initial survey was undertaken to assess attitudes to the use of electronic patient reported outcomes in clinical trials. Participants in the survey were asked whether they would be interested in being involved in a focus group relating to the design of the SWAT. These groups provided feedback on the user friendliness of the ePRO system, potential amendments to the system for greater acceptability amongst patients and provided insights into the potential level of guidance required to be provided to participants in the SWAT to help them to use the system. Members of the initial focus group were invited to join the patient and public oversight committee to oversee the remainder of the project and advise on study progress and results dissemination.

Patient advocates were involved in protocol design including methodology, design of the electronic system, patient information sheet and consent form, participant electronic questionnaire guidance, demographics questionnaire and participant feedback survey, and are represented on the SMG and patient and public oversight committee.

12.3. ETHICS APPROVALS

The study will not commence at any participating site until the required approvals are in place. ICR-CTSUs, on behalf of the Sponsor, will ensure that the study has received ethics approval from a research ethics committee (REC) for multi-centre studies, HRA approval and relevant NHS Permissions. Before recruiting patients, the Principal Investigator at each site is responsible for obtaining local approvals.

12.4. STUDY CONDUCT

This study will be conducted according to the approved protocol and its amendments, supplementary guidance and manuals supplied by the Sponsor and in accordance with the UK Policy Framework for Health and Social Care and the principles of GCP.

12.5. INFORMED CONSENT

The Principal Investigator retains overall responsibility for the conduct of research at their site; this includes obtaining informed consent from participants. They must ensure that any person delegated responsibility to participate in the informed consent process is duly authorised, trained and competent to do so in accordance with the ethically approved protocol, principles of Good Clinical Practice and Declaration of Helsinki. The Principal Investigator can be any suitably qualified healthcare professional.

Patients should be asked to sign the current ethics approved SPRUCE consent form at study entry after receiving both verbal and written information about the trial, having been given sufficient time to consider this information. All consent forms must be countersigned by the Principal Investigator or a designated individual. If consent is taken remotely, the date of remote consent should be recorded in the participant's medical notes and on the consent form once received.

A signature log of delegated responsibilities, listing the designated individuals and the circumstances under which they may countersign consent forms, must be maintained at the participating site. This log, together with original copies of all signed patient consent forms, should be retained in the Site Investigator File and must be available for inspection. The current ethics approved SPRUCE patient

information sheets should be provided in addition to any standard patient information sheets that are provided by the site and used in routine practice.

12.6. PATIENT CONFIDENTIALITY

Patients will be asked to consent to their full name being collected at study entry in addition to their date of birth, address, and email address (if applicable).

Each investigator should keep a separate log of all participants' study IDs, names, postal and email addresses and hospital numbers. The investigator must retain study documents (e.g. participants' written consent forms) in strict confidence. The investigator must ensure the participants' confidentiality is maintained at all times.

Representatives of ICR-CTSU will require access to participants' hospital notes for quality assurance purposes. ICR-CTSU will maintain the confidentiality of participants at all times and will not reproduce or disclose any information by which participants could be identified.

